8 STUDY ASSESSMENTS AND PROCEDURES

- Study procedures and their timing are summarized in the SoA ([Table 1](#)). Protocol waivers or exemptions are not allowed.
- Severe, clinically significant safety concerns should be discussed with the sponsor or designee immediately upon occurrence or awareness to determine if the subject should continue or discontinue study intervention.
- Adherence to the study design requirements, including those specified in the SoA ([Table 1](#)), is essential and required for study conduct.
- All screening evaluations must be completed and reviewed to confirm that potential subjects meet all eligibility criteria. Procedures conducted as part of the subject's routine clinical management (eg, blood count) and obtained before signing of the informed consent/assent forms may be utilized for screening or baseline purposes, provided the procedures met the protocol-specified criteria and were performed within the time frame defined in the SoA ([Table 1](#)).
- In person visits are the preferred approach to the study visits where in person evaluation is designated per the SoA; however, due to COVID-19, a virtual visit or home health visit may need to be performed. The Screening and Baseline Visits are not permitted to be conducted virtually. The medical monitor should be contacted to provide approval for a virtual visit(s) to be conducted instead of an in person (or home health visit, if arranged) visit. This permission should be documented and obtained prior to the visit(s). In case of a virtual visit, assessments should be completed over video, and the subject should submit photographs of areas of involvement to the site if possible. The conduct of a virtual or home health visit instead of in person visit should be captured in the eCRF.
- If necessary, arrangements may be made for subjects to return study drug by alternative methods, eg, mail, courier.

8.1 General Study Periods

8.1.1 Screening, Enrollment, and/or Randomization

A properly executed, written, informed consent will be obtained from each subject or subject's parent/guardian (for adolescents) and assent (for adolescents) prior to entering the study. Information will be given in both oral and written form and subjects must be given ample

opportunity to inquire about the details of the study. The inclusion and exclusion criteria will be reviewed to assess subject eligibility.

8.1.1.1 Demography

Subjects' demographic information including age, sex (gender assigned at birth), birthdate, race, and ethnicity will be collected at the Screening Visit.

8.1.1.2 Medical History

Subjects will be asked about their medical history at the Screening Visit and Baseline Visit (Day 1) to determine eligibility and safe participation in the study.

8.1.1.3 Atopic Dermatitis History

Subjects will be asked about their AD history at the Screening Visit and Baseline Visit, including approximate date of diagnosis and prior therapies for AD in the last 6 months. Subjects will be asked about current and recent prior medications. The medication name, dosing, frequency, route, start and stop dates, and indication will be recorded at the Screening Visit. Any changes in concomitant medications throughout the duration of the study will be noted.

8.1.2 Treatment Period

The treatment period begins on Day 1 when the first dose of TER-101 2.75% ointment or ointment vehicle is topically administered to a subject.

8.2 Efficacy Assessments

The below assessments will be used to assess overall AD disease severity. Planned time points for all overall baseline AD severity assessments are provided in the SoA (Table 1). Additional information on these instruments may be found at the Harmonizing Outcome Measures for Eczema website (<http://www.homeforeczema.org/>).

8.2.1 Investigator Global Assessment

The IGA is a 5-point scale that provides a global clinical assessment of overall AD severity based on an ordinal scale. The assessment is static, meaning that the evaluation is done without reference to any other time point.

0 = Clear: minor residual hypo/hyperpigmentation; no erythema or induration/papulation; no oozing/crusting.

1 = Almost clear: trace faint pink erythema, with barely perceptible induration/papulation and no oozing/crusting.

2 = Mild: faint pink erythema with mild induration/papulation and no oozing/crusting.

3 = Moderate: pink-red erythema with moderate induration/papulation with or without oozing/crusting.

4 = Severe: deep or bright red erythema with severe induration/papulation and with oozing/crusting.

8.2.2 Eczema Area Severity Index

The EASI is a scoring system that measures 4 clinical signs, the extent of BSA involved, over 4 separate areas (head/neck, trunk, upper extremities, and lower extremities). Total EASI scores range from 0 to 72.

The 4 clinical signs are:

- Erythema
- Induration/papulation
- Excoriation
- Lichenification

And each feature is graded for each region on a 4-point severity scale of 0 to 3, as below, with:

- 0 = absent
- 1 = mild
- 2 = moderate
- 3 = severe

The investigator or qualified assessor will enter the value for erythema, induration/papulation, excoriation and lichenification and extent of BSA for each region on the eCRF page. The EASI score will be calculated by the sponsor/designee. See Appendix 6 ([Section 10.6](#)).

8.2.3 Total Body Surface Area

The TBSA involved with AD will be determined. The subject's palm and fingers with fingers together represent approximately 1% of the TBSA.

8.2.4 Itch Numeric Rating Scale

The WI-NRS asks subjects to report their worst itch (maximal intensity) during the last 24 hours on an 11-point NRS, ranging from 0 = "no itch at all" to 10 = "worst itch you can imagine". This will be recorded by the subjects daily in the e-diary.

8.2.5 Photographs

Standardized photographs of up to 4 representative areas will be obtained at Baseline, Day 15, and Day 29. The areas photographed at baseline will be photographed on Day 15, Day 29. Details regarding photography will be supplied in the Study Reference Manual.

8.3 Safety Assessments

Safety assessments will include the following:

- Monitoring and recording of all reported AEs.
- Physical examinations, including height and body weight measurements.
- Periodic measurement of vital signs.
- ECG.
- Assessment of local tolerability.
- Clinical laboratory tests.
- Urine pregnancy tests.

Planned time points for all safety assessments are provided in the SoA ([Table 1](#)).

8.3.1 Physical Examination, Height, and Body Weight

A physical examination including a thorough skin examination will be conducted by the investigator at the Screening and Baseline Visits to ensure that the subject does not have conditions that would interfere with participation in the study.

A complete physical examination will include, at a minimum, assessments of the cardiovascular, respiratory, gastrointestinal systems. Height and body weight will also be measured and recorded at Screening. Physical examinations will only be performed at the indicated visits per the SoA. For all other visits during the study, physical examinations will only be performed when there is a complaint from the subject. Clinically significant abnormal findings from the physical examinations after baseline will be reported as AEs; prior to baseline, they will be reported as interval history.

8.3.2 Vital Signs

At in person visits at screening, baseline, Day 15, and Day 29, vital signs will be collected.

- Blood pressure and pulse measurements will be assessed in a sitting position with a completely automated device. Manual techniques will be used only if an automated device is not available.
- Blood pressure, pulse measurements, and temperature (to be taken before blood collection for laboratory tests) are strongly recommended to be preceded by at least 5 minutes of rest with the subject in a quiet setting without distractions (eg, television, cell phones).

8.3.3 Electrocardiogram

At screening and Day 29/EOT, a single 12-lead ECG with the subject in a supine position will be performed. The ECG is strongly recommended to be preceded by at least 10 minutes of rest with

the subject in a quiet setting without distractions (eg, television, cell phones) and before any blood sampling procedures.

8.3.4 Local Tolerability

At baseline and visits on Days 15 and 29, the investigator will assess erythema at the application sites. In addition, at baseline and visits on Days 15 and 29, subjects will be asked about any symptoms (pruritus, burning/stinging) following the last study drug application (see SoA, [Table 1](#)). Each feature will be scored from 0 to 3 as per the table in [Section 10.7](#). Care should be made as much as possible to distinguish local tolerability findings from the underlying AD.

8.3.5 Adherence to Study Agent

Adherence with twice daily application of the study agents will be monitored using an e-diary in which the subject will record date and time of application. The e-diary will be dispensed at the Baseline Visit and collected and reviewed at each visit. Adherence will also be monitored by weighing the medication tubes at the Baseline Visit prior to dispensing the study medication to the subject, and at in person visits on Day 15 and Day 29. If the subject has missed more than 2 or more doses in a 7-day period due to reasons related to noncompliance, then study staff will re-emphasize the importance of medication adherence. If the subject continues to consistently miss doses, other than for treatment hold due to local application site or tolerability concerns as described in [Section 6.2](#), then the sponsor should be notified, and the investigator and sponsor may consider discontinuing the subject for noncompliance, as per [Section 7.1](#). Subjects should also be queried by site staff at in person visits that the investigational product is being applied correctly.

8.3.6 Clinical Safety Laboratory Assessments

- See [Section 10.2](#) and the laboratory manual for the clinical laboratory tests to be performed and to the SoA ([Table 1](#)) for the timing and frequency.
- The investigator must review the laboratory report, document this review, and record in the AE section of the eCRF any clinically relevant changes occurring during the study. The laboratory reports must be filed with the source documents. Clinically significant abnormal laboratory findings are those that are not associated with the underlying disease, unless judged by the investigator to be more severe than expected for the subject's condition.
- All laboratory tests with values considered clinically significantly abnormal during participation in the study should be repeated until the values return to normal or baseline; or are no longer considered clinically significant by the investigator or medical monitor.
 - If such values do not return to normal/baseline within a period of time judged reasonable by the investigator, the etiology should be identified, and the sponsor notified.
 - All protocol-required laboratory assessments, as defined in [Section 10.2](#), must be conducted in accordance with the laboratory manual and the SoA ([Table 1](#)).

- If laboratory values from non-protocol specified laboratory assessments performed at the institution's local laboratory require a change in subject management or are considered clinically significant by the investigator (eg, SAE or AE), then the results must be recorded in the eCRF.

8.4 Adverse Events and Serious Adverse Events

The definitions of an AE or SAE can be found in [Section 10.3](#).

AE(s) will be reported by the subject.

The investigator and any qualified designees are responsible for detecting, documenting, and recording events that meet the definition of an AE or SAE and remain responsible for following up on any AEs that are serious, considered related to the study intervention or study procedures, or that caused the subject to discontinue the study (see [Section 7](#)). Note that lack of efficacy of the investigational therapy should not be considered an AE.

AEs related to the skin should clearly be designated if related to underlying condition and if related to the application site in the eCRF.

8.4.1 Time Period and Frequency for Collecting Adverse Events and Serious Adverse Events Information

AEs or SAEs occurring in the 30-day period following the last dose of investigational product should be reported, regardless of causality. SAEs occurring after this 30-day period should be reported only if considered related to investigational product or a study-related procedure.

SAEs will be collected from the signing of the informed consent form (ICF) until the end of treatment at the time points specified in the SoA ([Table 1](#)).

Medical occurrences that begin before the start of study intervention but after obtaining ICF will be recorded on the Medical History/Current Medical Conditions section of the eCRF, not the AE section, unless related to a study specific procedure.

All SAEs will be recorded and reported to the sponsor or designee immediately and under no circumstance should this exceed 24 hours, as indicated in [Section 10.3](#). The investigator will submit any updated SAE data to the sponsor within 24 hours of it being available.

Investigators are not obligated to actively seek AEs or SAEs after conclusion of the study participation. However, if the investigator learns of any SAE, including a death, at any time after a subject has been discharged from the study, and he/she considers the event to be reasonably related to the study intervention or study participation, the investigator must promptly notify the sponsor.

8.4.2 Method of Detecting Adverse Events and Serious Adverse Events

The method of recording, evaluating, and assessing causality of AEs and SAEs and the procedures for completing and transmitting SAE reports are provided in [Section 10.3](#).

Care will be taken not to introduce bias when detecting AEs and/or SAEs. Open-ended and nonleading verbal questioning of the subject is the preferred method to inquire about AE occurrences.

8.4.3 Follow-up of Adverse Events and Serious Adverse Events

After the initial AE/SAE report, the investigator is required to proactively follow each subject at subsequent visits/contacts. All SAEs will be followed until resolution, stabilization, the event is otherwise explained, or the subject is lost to follow-up (as defined in [Section 7.3](#)). Further information on follow-up procedures is given in [Section 10.3](#).

8.4.4 Regulatory Reporting Requirements for Serious Adverse Events

- Prompt notification by the investigator to the sponsor of an SAE is essential so that legal obligations and ethical responsibilities towards the safety of subjects and the safety of a study intervention under clinical investigation are met.
- The sponsor has a legal responsibility to notify both the local regulatory authority and other regulatory agencies about the safety of a study intervention under clinical investigation. The sponsor will comply with country-specific regulatory requirements relating to safety reporting to the regulatory authority, IRB, and investigators.
- Investigator safety reports must be prepared for suspected unexpected serious adverse reactions according to local regulatory requirements and sponsor policy and forwarded to investigators as necessary.
- An investigator who receives an investigator safety report describing an SAE or other specific safety information (eg, summary or listing of SAEs) from the sponsor will review and then file it along with the IB and will notify the IRB, if appropriate, according to local requirements.

8.4.5 Pregnancy

- Details of all pregnancies in female subjects and, if indicated, female partners of male subjects will be collected after the start of study intervention and at all other timepoints specified in the SoA ([Table 1](#)).
- If a pregnancy is reported, the investigator should inform the sponsor within 24 hours of learning of the pregnancy and should follow the procedures outlined in [Section 10.8](#).
- Pregnancy itself is not considered an AE, but if the study drug is suspected of causing contraceptive failure then contraceptive failure should be recorded as an AE.

- Abnormal pregnancy outcomes (eg, spontaneous abortion, fetal death, stillbirth, congenital anomalies, and ectopic pregnancy) are considered SAEs.

Sexually active males and females must use appropriate contraception as indicated in [Section 10.8](#). The use of contraception are strongly recommended to be discussed at each visit.

8.4.6 Adverse Events of Special Interest

There are no AEs of special interest for this study.

8.5 Treatment of Overdose

The Sponsor does not recommend specific treatment for an overdose; however, any skin to which study drug was applied should be thoroughly washed with cleanser and water to remove any drug remaining on the skin. Treatment of overdose should consist of general supportive measures.

In the event of a suspected overdose, the investigator should:

1. Contact the medical monitor immediately.
2. Closely monitor the subject for any AE/SAE and laboratory abnormalities.
3. Document the quantity of the excess dose as well as the duration of the overdose in the eCRF.

Decisions regarding dose interruptions or modifications will be made by the investigator in consultation with the medical monitor based on the clinical evaluation of the subject.

8.6 Pharmacokinetics

Blood draws for PK evaluation should be done at least 4 hours after last study drug application in accordance with the SoA ([Table 1](#)). The date, time of last application should be recorded on eCRF page.

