1.3 Schedule of Activities (SoA)

Table 1: Schedule of Activities

Period	Screening	Baseline	Treatment Period			Notes
			1	2	3	
Visit	1	2	3	4	5	
Visit Day and Window	D-35 to D-1	Day 1	D8 ± 3 days (Phone)	D15 ± 3 days	D29/ETV ^a ± 3 days	
Informed consent	X					Informed consent will be obtained from adult subjects and parent/guardian of subjects age 12 – 17; assent will be obtained from any subject age 12 – 17.
Demographics	X					
Medical history, including AD history	X	X				Complete medical and AD history will be collected at screening and interval medical history (or any change from Screening Visit) collected at baseline.
Physical examination	X	X			X	Clinically significant abnormal findings from the physical examinations after baseline will be reported as AEs.
Vital signs	X	X		X	X	Blood pressure, pulse rate, and temperature strongly recommended to be measured after the subject has rested for ≥ 5 minutes seated.
Body weight, height		X				
Clinical laboratory tests ^b	X	X			X	
ECG ^c	X				X	ECG strongly recommended to be performed after the subject has rested in a supine position for ≥ 10 minutes.
Blood for PK ^d				X	X	Date/time of last dose should be recorded for PK blood draws.
Urine pregnancy test (WOCBP)	X	X			X	Urine pregnancy tests may be performed more frequently as required by local regulations. The use of contraception will be discussed at each visit.
AD assessments	X	X		X	X	Includes IGA, EASI, and TBSA (in this order).
Inclusion/exclusion criteria	X	X				Confirm subject meets all inclusion/exclusion criteria before randomization.
Emollient and cleanser review	X	X	X	X	X	Site should confirm the emollient and cleanser the subject plans to use during the study are acceptable.
Concomitant medications	X	X	X	X	X	

Period	Screening	Baseline	Treatment Period			Notes
			1	2	3	
Visit	D-35 to D-1	Day 1	D8 ± 3 days (Phone)	D15 ± 3 days	D29/ETV ^a ± 3 days	
AE recording	X	X	X	X	X	AEs will be monitored and recorded throughout the study, beginning at the time that informed consent has been obtained.
Photography		X		X	X	Baseline photographs will be obtained prior to study drug application. The same regions will be photographed through the study under same conditions.
Randomization		X				
Local tolerability		X		X	X	At baseline, tolerability will be assessed pre-dose and 15 minutes after the first dose and also at Days 15 and 29.

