Study drug application		X				1 st dose of study drug will be applied by site staff and the subjects instructed on application. All subsequent application will be at home through evening dose on Day 28.
Dispense study medication, Instructions for Use, e-diary		X		[X]		Study drug will be weighed at the Baseline Visit, prior to first dose. Additional study drug may be dispensed on Day 15 if needed.
Instruct on WI-NRS tool		X	X	X		
Review e-diary, WI-NRS for compliance			X	X	X	The e-diary will be reviewed at each visit.
Collect and weigh study drug.				X	X	Study drug (used and unused tubes) will be collected and weighed at in person visits on Day 15 and Day 29. Study drug will be returned to subject at Day 15 and not returned to subject at Day 29.

AE=adverse event; BID = twice daily; D = Day; e-diary = electronic diary; EASI = Eczema Area and Severity Index; ECG= electrocardiogram; IGA = Investigator Global Assessment; PK = pharmacokinetics; TBSA = Total Body Surface Area; WI-NRS = Worst Itch Numeric Rating Scale.

^aETV: Early Termination Visit. All assessments scheduled for Day 29 will be conducted in event subject early terminates from study.

^bClinical labs: Complete blood count with differential, chemistry will be conducted at screening, baseline, Day 29. Urinalysis will be conducted at screening only. If the clinical laboratories were obtained within 14 days of baseline (Day 1), the screening labs will be used as the baseline labs and do not need to be repeated.

^cThe screening ECG will be used as the baseline ECG.

^dPK blood draws should be done at least 4 hours after last study drug application. The date, time of last application will be recorded on electronic case report form page. Avoid drawing PK samples through study drug application site.

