3 OBJECTIVES AND ENDPOINTS

OBJECTIVES	ENDPOINTS
Primary	

 To assess the efficacy of TER-101 (2.75% w/w) ointment vs. vehicle in subjects aged 12 - 65 with mild to moderate AD 	
Primary Efficacy Endpoints
 
 Percent change in EASI from baseline at Day 29 
Secondary Efficacy Endpoints
 
 Percent change in EASI from baseline over time Percent change in individual components of EASI (erythema, induration/papulation, excoriation, lichenification) and by region (head, trunk, UE, LE) from baseline over time EASI-75, EASI-50 responder analysis over time Absolute change in EASI from baseline over time Change in IGA from baseline over time Change from baseline WI-NRS at Days 15, 29 (WI-NRS captured on e-diary daily) Responder analysis: Reduction of ≥ 3 in subjects with baseline WI-NRS ≥ 4 Change in TBSA affected from baseline over time
Secondary	

 To assess the safety and tolerability of TER-101 (2.75% w/w) ointment vs. vehicle in subjects with AD 	
 Safety: TEAEs, SAEs, VS, ECGs, laboratories Tolerability: Scored by investigator at baseline and post-baseline visits on 4-point scale (0 = none; 3 = severe) to include subscores for erythema, burning/stinging, pruritus.

 To assess systemic exposure to TER-101 (2.75% w/w) ointment after BID treatment for 28 days 	PK: systemic plasma trough levels of TER-101 on Days 15, 29

BID = twice daily; EASI = Eczema Area and Severity Index; EASI-50/75 = 50 or 75% reduction in EASI score from baseline; ECG = electrocardiogram; IGA = Investigator Global Assessment; LE = lower extremities; PK = pharmacokinetics; SAE = serious adverse event; TBSA = Total Body Surface Area; TEAE = treatment emergent adverse event; UE = upper extremities; VS = vital signs; WI-NRS = Worst Itch Numeric Rating Scale; w/w = weight for weight.

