4 STUDY DESIGN

4.1 Overall Design

This is a Phase 2a, randomized, double-blind, vehicle-controlled study assessing efficacy and safety, and local tolerability of TER-101 (2.75% w/w) ointment vs. its ointment vehicle topically twice daily in adolescent and adult subjects (age 12 - 65) subjects with mild to moderate AD.

Subjects will be randomized 1:1 to receive either TER-101 (2.75% w/w) ointment or vehicle. Both the subject and the investigator will be blinded to the treatment assignments.

Approximately 60 adolescent and adult subjects (age 12 – 65) are planned to be enrolled across approximately 12 clinical research sites in the United States. Institutional Review Board (IRB) approval will be obtained for each clinical research site prior to recruiting any subjects at the site.

The study will include up to a 35-day screening period prior to enrollment/baseline visit and a 28-day active treatment period. Subjects will apply assigned treatment to all areas affected by AD at baseline twice daily throughout the treatment period. If the subject develops new areas of AD, those areas will also be treated. Treatment areas will exclude the scalp, nose, mouth and eyes. Subjects may use bland emollients on non-affected body sites once daily. Rescue medications are not permitted.

Efficacy assessments will include the EASI, Investigator Global Assessment (IGA), Worst Itch Numeric Rating Scale (WI-NRS), and Total Body Surface Area (TBSA) affected. Safety and tolerability assessments will include reported adverse events (AEs), clinical laboratories, physical examinations, ECGs, and vital signs as well as a separate tolerability assessment for treated areas. Systemic exposure will be determined by measuring trough TER-101 levels on Day 15 and Day 29/End of Trial (EOT). Photographs of representative areas of AD will be obtained at baseline, Day 15, and Day 29/EOT. The study procedures and visit timelines are described in the Schedule of Activities (SoA; [Table 1](#)). An overview of the study design is presented in [Figure 1](#).

If there are no safety concerns identified in the study, but additional subjects are needed to reach 50 subjects completing the study for efficacy, then additional subjects may be enrolled and randomized.

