6.1.1 Study Treatment Application

TER-101 (2.75% w/w) ointment and ointment vehicle will be applied topically twice a day for 28 days, with at least 8 hours between applications. Subjects will apply sufficient study drug to provide a thin covering. A pea-sized amount (approximately 250 mg) should cover approximately 2% BSA. Additional instructions on application will be provide in the 'Instructions for Use' provided to each subject at randomization.

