9.4.5 PK Endpoints

- Summary of trough plasma TER-101 levels on Days 15, 29 in TER-101 treated subjects

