3.8 PK ANALYSES

Plasma concentration of the study drug will be summarized using descriptive statistics including number of subjects with plasma samples, number of assays with concentrations above lower limit of quantification (LLOQ), arithmetic mean, geometric mean, Std Dev, coefficient of variation (CV), minimum and maximum at each nominal visit (Day 15, Day 29). A concentration that falls below the LLOQ will be treated as zero in the summary. Analysis will be conducted on PKs.

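### PK samples labelled trough are not assured to be troughs: the only timing rule is a 4-hour minimum, and the by-visit summaries ignore the recorded time since last application

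*Protocol*

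**What the plan says.** Protocol section 3 and the SAP 1.1 objectives table give the endpoint as "PK: systemic plasma trough levels of TER-101 on Days 15, 29", under an objective about systemic exposure after 28 days of twice-daily use. Protocol 9.4.5 repeats the label: "Summary of trough plasma TER-101 levels on Days 15, 29 in TER-101 treated subjects".

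The sampling rule in Protocol 8.6, repeated in SoA footnote d, is "Blood draws for PK evaluation should be done at least 4 hours after last study drug application". Neither place gives a maximum or says where the draw falls relative to the next application. Both ask for the date and time of the last application to be recorded.

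Application is morning and evening (Protocol 4.1.3), "with at least 8 hours between applications" (Protocol 6.1.1). The SoA states: "All subsequent application will be at home through evening dose on Day 28". The final visit column is headed "D29/ETV ^a ± 3 days", so it spans Days 26 to 32, and an early-termination visit carries all Day 29 assessments, including the PK draw.

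SAP 3.8 plans descriptive statistics, ending with "minimum and maximum at each nominal visit (Day 15, Day 29". The PK analysis set in SAP 3.2.1 needs only one blood draw. Neither section uses the time of last application.

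**The concern.** A trough is the concentration at the end of a dosing interval. The rule admits samples well before that point and, at the last visit, samples days after dosing has stopped. A reader of the PK report would see one column per visit described as trough exposure, although each column can contain samples taken at quite different times.

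The two visits also differ by design. Dosing is ongoing throughout the Day 15 window, but has stopped for any Day 29 visit held after Day 28. A difference between the two by-visit summaries could therefore come from sampling time alone. The study uses a higher concentration for longer than the earlier trial, and these are its only two PK samples.

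**Working it through.** The documents give no maximum elapsed time, so there is no figure of theirs to reproduce. The range follows from the schedule.

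**Inputs from the documents**
- Minimum time from application to draw: 4 h (Protocol 8.6).
- Minimum interval between applications: 8 h (Protocol 6.1.1).
- Last application: evening of Day 28 (SoA).
- Visit windows: Day 15 ± 3 gives Days 12 to 18; Day 29 ± 3 gives Days 26 to 32 (SoA).

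**Assumptions**
- Evening application between 18:00 and 22:00; visit between 08:00 and 17:00. The documents give no clock times.

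**Lower end, either visit while dosing continues.** Application at 07:00 and draw at 11:00 is 4 h and complies. Since 4 h < 8 h, the sample precedes the end of even the shortest permitted interval.

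**Upper end, Day 29 visit held after Day 28.** Elapsed hours = 24 × (visit day − 28) + visit hour − evening hour. For Day 32, 20:00 to 08:00: 24 × 4 + 8 − 20 = 84 h.

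| Visit day | Shortest (22:00 to 08:00) | 20:00 to 08:00 | Longest (18:00 to 17:00) |
|---|---|---|---|
| 29 | 10 h | 12 h | 23 h |
| 30 | 34 h | 36 h | 47 h |
| 31 | 58 h | 60 h | 71 h |
| 32 | 82 h | 84 h | 95 h |

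**Day 15 visit.** Dosing is ongoing on Days 12 to 18. The range for an otherwise adherent subject is about 4 h (morning application, then draw) to about 23 h (applied at 18:00 the evening before, not yet applied when bled at 17:00: 24 + 17 − 18 = 23). The same holds for final visits on Days 26 to 28.

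**Early termination.** No limit is set on the time between the last application and this visit, so the elapsed time is unbounded.

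**Illustration only.** Assume mono-exponential decline with absorption complete by 4 h; neither this nor any half-life T is in the documents. Level relative to the 12 h value = 2^((12 − t)/T):

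| T | t = 4 h | t = 36 h | t = 84 h | 4 h level ÷ 84 h level = 2^(80/T) |
|---|---|---|---|---|
| 12 h | 1.59 | 0.25 | 0.016 | about 102 |
| 24 h | 1.26 | 0.50 | 0.125 | about 10 |
| 48 h | 1.12 | 0.71 | 0.35 | 3.2 |
| 96 h | 1.06 | 0.84 | 0.60 | 1.8 |

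The effect of sampling time runs from under 2-fold to about 100-fold over these half-lives, so the documents do not fix its size. They do not fix its direction either. Under the same assumptions with T = 12 h, a 21 h sample at Day 15 is 0.60 of the 12 h value. With T = 6 h, a 10 h sample on Day 29 is 2^(2/6) = 1.26 times it. If absorption is still under way at 4 h, the early-sample figures do not apply.

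**The case against.** The strongest reply is that this is a descriptive secondary endpoint in an exploratory Phase 2a study. PK goes into a separate report (SAP 2.4.4), no test of Day 15 against Day 29 is planned, and no decision rule depends on a concentration. SAP 2.4.4 and 3.8 speak of plasma levels and concentrations rather than troughs, and the time of last application is recorded, so the data can be sorted out later. All of that is true and limits the consequence. It does not remove the mismatch: the SAP's own objectives table keeps the trough label, and nothing in the plan says the recorded times will be used.

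Several stronger readings are tempting, and the documents do not support them:
- *That none of the samples is a trough.* A morning draw about 12 h after an evening application, before the next one, is a trough at either visit.
- *That Days 15 and 29 cannot be compared.* They can, using the recorded elapsed times. Only the planned by-visit summaries fail to support a comparison. Each visit is also summarised separately, so samples are not pooled across visits.
- *That about 84 h applies to PK samples generally.* It arises only at a late Day 29 visit.
- *That treatment holds lengthen the gap.* Protocol 6.2 holds treatment at the affected site only. Time since last application would grow only if every treated area were held.
- *That Day 15 overstates trough and Day 29 understates it.* Samples on either side of 12 h are possible at both visits, and the documents give no distribution of visit times.

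**Conclusion.** The point stands. Following the plan exactly can report non-trough concentrations as trough exposure. Compliant samples can be 4 h after application while dosing continues, and about 82 to 95 h after it at a Day 32 visit, the latter under the assumed clock times. Early-termination samples have no bound. The Day 15 range is narrower, about 4 to 23 h. The by-visit summaries mix these times, so a difference between them could reflect sampling time alone.

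How large such a difference would be, and in which direction, cannot be said, because neither a half-life nor an absorption profile is given. The fold-changes in the working are illustrations and do not estimate bias in this trial. No efficacy analysis is affected. The change is still worth making, because it bears on a stated objective and the data needed for it are already collected.

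**What to change.** **SAP 3.8.** Use the recorded date and time of last application to:
- state in advance the range of elapsed time that counts as trough (the sponsor should set it; 8 to 16 h is only an example);
- restrict the trough summary to samples in that range;
- list or plot every concentration against actual time since last application;
- keep late Day 29 and early-termination samples out of the trough summary.

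**Protocol.** Reconcile three items: the trough endpoint (sections 3 and 9.4.5), the 4-hour rule (SoA footnote d and 8.6) and the Day 29 visit window. How they are reconciled is for the sponsor; this point asks for no change to when subjects apply study drug.

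**Cost.** A short addition to SAP 3.8 and a protocol clarification, with no new data. The downside is that fewer samples count as troughs. With about 60 subjects randomised 1:1, roughly 60 ÷ 2 = 30 receive TER-101, so the restricted summary could be small. The plot against elapsed time keeps the remaining samples in view.
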